13.4. Eligibility of Subjects, Exclusions, and Missing Data

The number and proportion of subjects eligible for and compliant with each follow-up examination will be presented. Subjects who withdraw from the study will be tabulated with reasons for withdrawal.

Missing data, which in this instance is defined as data that was not entered into the EDC system for analysis, may have an impact upon the interpretation of the trial data.

The primary presentation of the results for the ITT population will be based on the observed data with multiple imputation for missing endpoint data using SAS PROC MI. This procedure uses an iterative modeling approach to generate estimates for patients who withdraw prematurely, incorporating multivariate imputation by fully conditional specification (FCS) methods. The discriminant function method will be used for classification variables. With the function method of classification, the missing values will be imputed sequentially in the following order: age, gender, aneurysm diameter and location (ICA: yes or no). Additional sensitivity analyses will also be conducted using the last observation and the post-procedure observation carried forward. A tipping point analysis will also be conducted.

Rules for imputing a full date for interventions with incomplete or missing start-dates will be addressed in detail in the Statistical Analysis Plan.

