5.1.1.1. Primary Endpoints

5.1.1.1.1. Primary Effectiveness Endpoint

The following will be assessed for the primary effectiveness endpoint:

 \circ Incidence of complete aneurysm occlusion (Raymond Roy Scale Class 1) without significant parent artery stenosis (≤ 50%) or retreatment of the target aneurysm at 1-year post-procedure.

Complete occlusion and parent artery stenosis will be adjudicated by the Imaging Core Laboratory. Retreatment will be assessed per site records.

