13.3. Analysis Populations

To ensure adequate representation patient with large and giant aneurysms must be enrolled. All primary and secondary endpoints will be analyzed both on an ITT and PP basis. All summarizations and tabulations will be conducted on the ITT population, defined below.

Intent-To-Treat Population: All subjects who were consented and in whom deployment of the Pipeline[™] Vantage Device was attempted (i.e., puncture at the arterial access site), independent of the procedure being completed successfully.

Subject will not be considered part of the ITT population if the puncture at the arterial access site for deployment of Pipeline[™] Vantage Device was not successful. If the puncture at the arterial access site for deployment of Pipeline[™] Vantage Device was successful, the subject will be considered part of the ITT population. Consented subjects who withdraw consent prior to undergoing the study procedure or are found not to meet the inclusion/exclusion criteria prior to undergoing the study procedure, will not be included in the ITT population.

The ITT population will be the primary population for all analyses.

PR-NV16099

The PP population defined below will be used for sensitivity analyses and to provide outcomes for subjects with observed data.

Per-Protocol Population: Per-protocol population is ITT subjects excluding the following subjects:

- Subjects with use of more than 1 treatment device (e.g., coils) other than Pipeline[™] Vantage device during index procedure
- Subjects with failed implantation of study device at index procedure
- Subjects assessed as mRS ≥3 at baseline by independent and certified assessors

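### Section 13.4 imputes missing 1-year effectiveness data without separating death from withdrawal, so a device- or procedure-related death can be credited as about two-thirds to three-quarters of a success

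*Combined protocol and SAP*

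**What the plan says.** Section 13.4 sets the primary analysis: "The primary presentation of the results for the ITT population will be based on the observed data with multiple imputation for missing endpoint data". Missing data are "defined as data that was not entered into the EDC system for analysis". The procedure is described as one to "generate estimates for patients who withdraw prematurely", and the variables listed for it are "age, gender, aneurysm diameter and location (ICA: yes or no"). Carry-forward of the last and of the post-procedure observation, and a tipping-point analysis, are planned as sensitivity analyses.

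Section 13.3 says "The ITT population will be the primary population for all analyses". A subject enters that population at successful arterial puncture, whatever follows.

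Section 5.1.1.1.1 builds the endpoint from complete occlusion, absence of significant parent artery stenosis, and absence of retreatment; the last part reads "or retreatment of the target aneurysm at 1-year post-procedure". Occlusion and stenosis come from the core laboratory. For the third component, "Retreatment will be assessed per site records". Death is not a component. No section says how a subject who dies before the 1-year imaging enters the effectiveness analysis.

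**The concern.** A subject who dies three weeks after the procedure is in the ITT denominator, has no 1-year DSA and so meets the definition of missing. The variables named for the imputation do not include death, stroke, rupture or the 180-day imaging. The model therefore gives this subject about the success probability of a survivor with similar baseline values.

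A subject lost to follow-up has an unknown result. A subject killed by the procedure does not: durable occlusion was never achieved. Crediting part of a success moves the effectiveness estimate in the device's favour for the very events that count against it in the safety analysis. In a single-arm trial tested against a fixed 50% threshold, no control arm offsets this.

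**Working it through.** **Inputs**
- Design: N = 100, threshold 50%, one-sided 2.5%, assumed rate 65% (sections 13.2 and 13.8.2.1).
- Predecessor effectiveness rates: SHIELD 71.67%, PFLEX 73.62%, PREMIER 76.71% (sections 4.2.5, 4.2.7, 4.2.8).
- Deaths: PREMIER 1/141, SHIELD 2/204 (both neurological), PFLEX 0/50. Total 3/395 = 0.76%.
- IntrePED neurological mortality: 30/793 = 3.8% (section 4.2.3).

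**1. The plan's own figure.** The exact lower bound is L(x, n) = the 2.5% quantile of Beta(x, n - x + 1).
- L(60, 100) = 49.72% and L(61, 100) = 50.73%, so the cutoff is 61.
- P(X >= 61 | n = 100, p = 0.65) = 82.76%, against 82.8% stated.
- For N = 80 and 67% (rate from the Synopsis), the cutoff is 50 and power is 83.54%, against 83.5% stated.

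The lower bound is used throughout. Section 13.8.2.1 words the criterion on the upper bound, but the stated power reproduces with the lower one. That is a separate matter.

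**2. Credit per death.** Suppose there are d deaths and x successes among 100 - d imaged survivors, and write q = x/(100 - d). If the imputation ignores death, each death has an expected imputed value of about q. On the documents' figures q runs from 0.65 (design) to 0.767 (PREMIER).

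**3. Inflation of the rate.** Deaths as failures give x/100. Deaths imputed give (x + dq)/100. The difference is d x q percentage points per 100 subjects.
- 1 death: 0.65 to 0.77
- 2 deaths: 1.3 to 1.5
- 4 deaths: 2.6 to 3.1
- At 3/395 (0.76 per 100): 0.76 x 0.65 = 0.49 to 0.76 x 0.767 = 0.58
- At 3.8 per 100: 3.8 x 0.65 = 2.5 to 3.8 x 0.767 = 2.9

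**4. Boundary example.** There are 60 successes among 99 imaged survivors, and one death.
- Death as failure: 60/100, bound 49.72%, not met.
- Death imputed: 60 + 60/99 = 60.61, bound about 50.3%, met.

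The bound for a fractional count is the beta quantile, used as an approximation to the pooled result.

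**5. Effect on the test.** Imputation is approximated by analysing survivors only. Each cell shows imputed / failure. Type I error is taken where the true rate, with deaths as failures, is exactly 50%.

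| Deaths per 100 | Power, survivors at 65% | Power, survivors at 71.67% | Type I error |
|---|---|---|---|
| 1 | 84.65% / 79.24% | 99.35% / 98.85% | 2.78% / 1.71% |
| 2 | 81.37% / 75.28% | 99.05% / 98.35% | 2.71% / 1.66% |
| 4 | 79.89% / 66.10% | 98.86% / 96.76% | 4.07% / 1.55% |

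**6. Chance that the verdict differs.** This sums, over d ~ Binomial(100, mortality), the probability that survivors alone pass while x is at most 60.
- Mortality 0.8%: 3.3% if survivors succeed at 65%, 0.3% at 71.67%, 0.01% at 76.71%.
- Mortality 3.8%, survivors at 71.67%: 2.7%.

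**The case against.** **The text never says that deaths are imputed.** It speaks of patients who withdraw, and a reader might go too far in inferring a deliberate decision to score deaths as likely successes. The documents do not support that inference: the plan is silent on death. What stands against the objection is that the definition of missing is broad enough to cover a death and nothing takes it out.

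**The detailed SAP promised in section 13.1 may settle it.** It may; it is not among the documents. But section 13.4 expressly defers to it only the imputation of incomplete dates, and announces no rule for deaths.

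**The endpoint is anatomical, and neurological death is already a primary safety event.** This is fair, and counting death as failure is partly a choice of estimand. Reporting a death under safety still does not justify a success credit under effectiveness.

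**Retreatment.** A reader might infer that a retreated subject without a 1-year DSA could also be imputed as a success. The documents do not support this. Retreatment is an endpoint component, is entered on its own case report forms (section 9.8), and so is already a known failure. A sentence confirming this is enough.

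**Sensitivity analyses.** For an early death both carry-forward analyses would use the Day 0 image, and the tipping-point analysis can show how far the conclusion depends on imputed values. Neither changes the primary result, none is specified with deaths as failures, and a 180-day occlusion could be carried forward past a later death.

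**Size.** IntrePED is a poor guide to 1-year ICA mortality: it was retrospective, had a median follow-up of 19.3 months, and included various locations and some ruptured aneurysms. This stands. The three closer studies imply about one death per 100.

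**Conclusion.** The concern holds as a gap with a known direction. As written, 13.4 lets a neurological, procedure-related or device-related death before the 1-year DSA be imputed at roughly the survivors' success rate, and this can only raise the effectiveness estimate. The expected inflation is about 0.6 points at the death rate of the closest predecessors, and about 3 points at the IntrePED rate.

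A reader might infer that the trial's conclusion is in danger. The figures do not support that. If survivors succeed at the predecessors' rates, the verdict almost never changes. It becomes sensitive only near 61/100, or at a survivor rate close to the 65% design value combined with several deaths.

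This rests on four assumptions: the imputation uses only the named baseline variables; deaths do not cluster in baseline groups with lower occlusion; the pooled analysis behaves much like a survivors-only analysis; and the SAP adds no death rule. The 3/395 counts all deaths, so the share caused by the device, the procedure or a neurological event may be smaller. The change should be made because it is cheap and the bias favours the device.

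**What to change.** Add three statements to section 13.4 and carry them into the SAP before any analysis:

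1. A subject with a CEC-adjudicated neurological, procedure-related or device-related death before the 1-year imaging is a primary effectiveness failure and is not imputed.
2. A recorded retreatment of the target aneurysm before the 1-year assessment is a failure whether or not 1-year imaging exists. This confirms the existing endpoint definition.
3. Multiple imputation is limited to subjects whose status is unknown (withdrawal, loss to follow-up, missing or unreadable imaging) and to deaths adjudicated as unrelated.

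The cost is a few lines of text and no new data. The CEC already adjudicates neurological death and event causality (sections 5.1.1.1.2 and 12.1), and sites already record retreatment. The downside is a slightly lower reported rate and some loss of power if deaths occur: with one death and survivors at 65%, power is 79.2% rather than the planned 82.8%.

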4.2.2. PUFs: Pipeline[™] Embolization Device for Uncoilable or Failed Aneurysms

The PUFs study was a multi-center, prospective, single-arm trial to evaluate the safety and effectiveness of the Pipeline^M Embolization Device (PED) in complex large and giant intracranial aneurysms. One hundred seven subjects with large and giant unruptured wide-necked aneurysms in the petrous to the superior hypophyseal segment of the ICA were treated with the PED. The aneurysms measured \geq 10 mm in diameter and had either a neck \geq 4 mm or no discernable neck. A total of 104 subjects with 106

PR-NV16099

PR-NV16099

Version C Page 38 of 144

Medtronic

aneurysms were included in the primary effectiveness cohort and evaluated by an independent core lab. Of the 106 aneurysms, 78 demonstrated complete occlusion without major stenosis at 180 days (73.6%; 95% posterior probability interval: 64.4%–81.0%). At one year, 86.8% (79/91) of the target aneurysms were completely occluded. This rate increased to 95.2% (59/62) complete occlusion at five years. There were no cases of aneurysm recurrence. The primary safety endpoint was the occurrence of major ipsilateral stroke or neurologic death at 180 days, which occurred in six of the 107 subjects (5.6%; 95% posterior probability interval: 2.6%–11.7%). At five year follow-up, and the rate of major ipsilateral stroke or neurologic death remained 5.6%.⁹²

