4.2.4. ASPIRe: Aneurysm Study of Pipeline[™] in an Observational Registry

ASPIRe was a prospective, multi-center, single-arm, post-market registry of 191 intracranial aneurysm patients with 207 aneurysms from 28 worldwide centers who underwent PED treatment. The 207 aneurysms in the study had a median follow-up duration of 6.6 months. The majority of aneurysms treated were saccular and overall average size of treated aneurysms was 14.5 mm.

Neurological morbidity was 6.8% (13/191) and the neurologic mortality rate was 1.6% (3/191). The combined rate of neurological morbidity and mortality was 6.8% (13/19), with the most common major adverse event of interest being intracerebral hemorrhage (3.7%, 7/191) followed by ischemic stroke (1.6%, 3/191). Most of the major adverse events (6.3%, 12/191) occurred in the early post-operative phase within the first 30 days following PED treatment.

Aneurysm occlusion was assessed by an independent core lab according to the Scale of Roy at last visit for all subjects with imaging follow-up of at least 6 months. The median follow-up duration was 7.8 months and complete occlusion was reported in 75% of subjects (77/103).

The ASPIRe registry, as a comprehensive evaluation of PED use in the real world, confirmed that the PED is safe when used for the treatment of intracranial aneurysms in routine clinical practice, reporting a 6.8% rate of associated major morbidity and neurological mortality.

4.2.5. PREMIER: Prospective Study on Embolization of Intracranial Aneurysms with the Pipeline[™] Device

PREMIER was the first prospective, multicenter trial to evaluate the use of the Pipeline[™] device for the treatment of small and medium, unruptured aneurysms of the intracranial carotid and proximal vertebral artery. The study was conducted in 1 Canadian and 22 US centers.

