ADVANCE Clinical Investigation Plan Medtronic PR-NV16099 Version C Page 41 of 144 Medtronic

Occurrence of major stroke in the territory supplied by the treated artery or neurological death at 1-year post-procedure (primary safety endpoint) occurred in 3.23% of subjects. Major stroke in the territory supplied by the treated artery or neurological death at 30 days post-procedure due to procedural complications were observed in 2.9% (6/204) of subjects. No delayed intracerebral hemorrhage (>30 days to 1-year post-procedure) was observed (0.0%). Overall, the incidence of major stroke, neurological death, and delayed intracerebral hemorrhage in the SHIELD study was low. Through the 1-year follow-up, the rate for death was 1.0% (2/204) (same for neurological death), all stroke was 6.4% (13/204), disabling stroke as observed (including death) was 1.0% (2/200), and ICH was 4.4% (9/204). Summary of primary endpoints of SHIELD study is presented in **Table 4-1**.

Endpoints	Rates	2-sided 95% exact binomial confidence interval				
Primary Effectiveness Endpoint: Complete aneurysm ocdusion (defined as Raymond-Romparent artery stenosis (≤ 50%) or retreatment of the target a neurysm at 1-year post-proc		ut significant				
FAS# population (N=200)	71.67%	(64.95%,77.74%)				
ICA ⁺ -FAS population (N=149)	75.30%	(67.58%,81.99%)				
Primary Safety Endpoint : Occurrence of major stroke in the territory supplied by the treat 1-year post-procedure	ated artery or neu	rological death a t				
ITT* population (N=204)	3.23%	(1.27%,6.68%)				
ICA [†] population (N=153)	3.27%	(1.07%,7.46%)				
*Intention to Treat (ITT) population includes all consented subjects in whom deployment of the Pipeline [™] Shield device was attempted. For the ITT population, primary effectiveness endpoint analysis was based on Full Analysis Set (FAS) population and safety analysis was based on the ITT population. #Full Analysis Set (FAS) is defined as a subset of the ITT population including only those in whom the Pipeline [™] Shield device was implanted.						
†Internal Carotid Artery population (ICA population) is defined as a subset of ITT population that inclu Pipeline™ Shield device was implanted in the ICA (segments C2-C7). For the ICA population, primary based on FAS (referred to as ICA-FAS) and safety analysis was based on the ICA population.	•	•				

Table 4-1. Summary of Primary Endpoints of SHIELD Study

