9.15.1. Subject Withdrawal

All enrolled subjects have the right to withdraw their consent at any time during this study. All data collected until the time of subject withdrawal will remain in the study database and will be used for analysis. If a subject is withdrawn from the clinical study, the reason for withdrawal shall be recorded in the eCRF and in the subject's hospital record.

Whenever possible, the clinical site staff should obtain written documentation from the subject who wishes to withdraw his/her consent for future follow-up visits. If the clinical site staff is unable to obtain written documentation, all information regarding the subject's withdrawal must be recorded in the subject's medical record. In addition, the appropriate eCRFs must be completed for the subject and clear documentation of the subject's withdrawal should be provided to the Sponsor.

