13.2. Sample Size Determination

The target sample size for this clinical investigation is 100 patients enrolled and treated and followed for safety events with the expectation of having digital imagery at 1-year post-procedure on a minimum of 80 patients.

Sample size estimation for the primary safety endpoint was initially based on recommendations by the FDA considering the precision of the estimates. For the primary safety endpoint, the incidence of major stroke in the territory supplied by the treated artery or neurological death at 1 year, with an incidence as high as 8%, a sample size of 100 subjects will provide a precision of approximately ± 5.5%, which is considered to be reasonable.

The basis for establishing the a priori threshold for the primary safety endpoint at 14% is rooted in the derivations presented in the table presented below, predicated on a population for analysis of 100 patients (with up to 140 subjects enrolled). Simulations were prepared in SAS assuming an observed incidence in the ADVANCE IDE study of primary safety events ranging from 5.6% to 6.9%. Scenarios 1 through 9 reveal a power greater than 80% (**Table 13-1**).

Simulation Scenario	a priori Threshold (proportion)	Observed Incidence (proportion)	Actual Type 1 Error Rate	Power (percent)
1	0.14	0.0560	0.0492	89.19
2	0.14	0.0570	0.0492	88.29
3	0.14	0.0580	0.0492	87.36
4	0.14	0.0590	0.0492	86.38
5	0.14	0.0600	0.0492	85.37
6	0.14	0.0610	0.0492	84.32
7	0.14	0.0620	0.0492	83.23
8	0.14	0.0630	0.0492	82.11
9	0.14	0.0640	0.0492	80.96

Table 13-1. Estimated Power Over a Range of Possible Primary Safety Outcomes with 100 Patients (a priori threshold of 14%)

Medtronic Controlled Information

This document is electronically controlled

056-F275, v A Clinical Investigation Plan Template

ADVANCE Clinical Investigation Plan					
PR-NV16099)	Version C	Page 109 of 144		Medtronic
10	0.14	0.0650	0.0492	79).77
11	0.14	0.0660	0.0492	78	3.55
12	0.14	0.0670	0.0492	77.30	
13	0.14	0.0680	0.0492	76.02	
14	0.14	0.0690	0.0492	74	l.72

Although the power is less than 80 when the incidence of safety events is 6.5% or higher, the power is still adequate when contrasted against the actual upper bound of the 1-sided 97.5% exact binomial confidence interval. Specifically, if 7 of the 100 patients experience a primary safety event, the upper bound of the 1-sided 97.5% exact binomial confidence interval would be 13.89% and below the 14% threshold.

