13.8.2.2. Primary Safety Endpoint

The primary safety endpoint is 1-year incidence of major stroke in the territory supplied by the treated artery or neurological death. The incidence will be summarized using counts and percentages; the 1-sided

PR-NV16099	Version C	Page 113 of 144		Medtronic
------------	-----------	-----------------	--	-----------

upper bound of the 97.5% confidence limit for the incidence will be evaluated relative to the a priori safety threshold of 14%. Given the primary safety endpoint reported in PMA P100018 was 5.6%, an incidence of ≤7% for the primary safety endpoint would be considered clinically acceptable within the confines of a study of this general size. The hypothesis for evaluating the primary safety endpoint will be evaluated according to the following 2 requirements:

Requirement 1: The incidence of primary safety events must be \leq 7%, and

Requirement 2: The null hypothesis must be rejected in favor of the alternative:

 H_{o} : Incidence at 1-year post-procedure of major stroke and/or neurological death is \geq 14.0%

 H_a : Incidence at 1-year post-procedure of major stroke and/or neurological death is < 14.0%

If the incidence of primary safety events is ≤7% and the upper bound of the 1-sided 97.5% exact binomial confidence interval is <14%, the primary safety endpoint will have been met.

All eligible patients will undergo follow-up at 12 months.

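### Section 13.4 does not exempt primary safety from baseline-only multiple imputation; applied there, it gives event-free withdrawals the full 1-year risk again and can fail the 7% rule near its boundary

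*Combined protocol and SAP*

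**What the plan says.** Section 13.3 makes the ITT population primary for every analysis. Section 13.4 says the main ITT results will use observed data plus multiple imputation (SAS PROC MI) for missing endpoint data. The procedure is meant to "generate estimates for patients who withdraw prematurely". The only variables it names are age, gender, aneurysm diameter and location. Time on study and event status at exit are not mentioned, and no endpoint is excluded. Last-observation, post-procedure carry-forward and tipping-point analyses are planned as sensitivity analyses.

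The Synopsis (Statistical Analysis) places the imputation sentence in the effectiveness paragraph. Its safety paragraph, like section 13.8.2.2, speaks of recorded events, counts, percentages and an upper limit, and does not mention imputation.

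On withdrawals, section 9.15.1 states: "All data collected until the time of subject withdrawal will remain in the study database and will be used for analysis". Section 9.15 adds that withdrawn subjects are not replaced.

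On the decision rule, section 13.8.2.2 reads: "If the incidence of primary safety events is ≤7% and the upper bound of the 1-sided 97.5% exact binomial" confidence interval lies below 14%, the endpoint is met. Section 13.2 gives the planned number: "The target sample size for this clinical investigation is 100 patients enrolled and treated and followed for safety events".

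**The concern.** Because data up to withdrawal are kept, a subject who has a major stroke or neurological death before leaving is observed. Only subjects who were event-free at exit can have a missing 1-year safety outcome. An imputation model that sees only baseline variables cannot know this. It treats someone last seen well at month 9 like someone treated yesterday and assigns about the full 1-year risk, including the months already survived.

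Requirement 1 is a hard cut at 7% in about 100 subjects, and the plan's own boundary case is 7 events. A small upward shift in the estimate can therefore turn a pass into a fail because event-free subjects left the study.

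**Working it through.** **Inputs.** N = 100 (section 13.2). Rule: incidence at most 7%, and exact one-sided 97.5% upper bound below 14% (section 13.8.2.2). Reference rate 5.6% (section 13.8.2.2). The documents give no dropout figure for 1-year safety, so m = 1 to 20 is an assumed range. Its upper end is borrowed from the shortfall in 1-year imaging that section 13.2 tolerates (100 planned, at least 80 imaged).

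**Step 1: reproduce the plan's figure.** The Clopper-Pearson upper bound is the 0.975 quantile of Beta(x + 1, n - x). For 7/100 it is 13.892%, matching the plan's "confidence interval would be 13.89% and below the 14% threshold". For 8/100 it is 15.16%. With complete data the rule therefore means at most 7 events.

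**Step 2: expected incidence under baseline-only imputation.** If the covariates carry little information on outcome, each of m event-free dropouts is assigned a risk of about x/(100 - m). The expected incidence is

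[x + m·x/(100 - m)]/100 = x/(100 - m).

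The plan gives no pooling rule for the bound. The bounds below assume Clopper-Pearson at the fractional count 100x/(100 - m) with n = 100.

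| Events x | Dropouts m | Incidence | Upper bound | Rule |
|---|---|---|---|---|
| 7 | 0 | 7.00% | 13.89% | met |
| 7 | 1 | 7.07% | 13.98% | fails 7% |
| 7 | 2 | 7.14% | 14.07% | fails both |
| 7 | 5 | 7.37% | 14.36% | fails both |
| 6 | 10 | 6.67% | 13.47% | met |
| 6 | 15 | 7.06% | 13.97% | fails 7% |
| 5 | 20 | 6.25% | 12.93% | met |

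**Step 3: check by simulation.** Discriminant-function imputation with two continuous covariates and 50 imputations gave a mean of 7.07–7.08% for x = 7, m = 1, with 93–95% of simulated trials above 7%. For x = 7, m = 5 the mean was 7.37% and every trial exceeded 7%. For x = 6, m = 15 the mean was 7.05–7.11%, and 51–68% exceeded 7%. For x = 5, m = 20 at most 2% did. The formula is thus an expectation, and single trials scatter around it.

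**Step 4: chance of passing.** With X binomial (100, p) and all dropouts late and event-free:

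| True rate | X ≤ 7 (no inflation) | X ≤ 6 (m = 1–14) | X ≤ 5 (m = 15–28) |
|---|---|---|---|
| 5.6% | 80.2% | 67.2% | 50.9% |
| 6.0% | 74.8% | 60.6% | 44.1% |

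These do not match Table 13-1 (89.19% at 5.6%), because that table reproduces only if 8 events are allowed (type 1 error 0.0492). The stated 97.5% bound allows 7.

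**Step 5: the alternative near the boundary.** Kaplan-Meier with 7 events and one dropout after all of them gives 7.00%. If the dropout falls just before the last event, survival is 0.94 × 92/93 = 0.92989 and the incidence is 7.01%. If it precedes all events, the incidence is 7/99 = 7.07%. Kaplan-Meier therefore lies between x/100 and x/(100 - m), according to the observed timing.

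**The case against.** The strongest reply is that imputation may never have been meant for safety. The Synopsis ties it to effectiveness, and safety is described by counts and percentages. On that reading a withdrawn subject with no recorded event counts as event-free, and nothing is inflated. Section 13.1 also defers detail to a later SAP. This stands as far as intent goes. A reader might infer from section 13.4 that the primary safety result is biased by construction, but the documents do not settle that. What remains is that section 13.4, read alone, covers safety and no text says otherwise.

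The planned last-observation analysis returns x/100 for event-free dropouts. That is a fair mitigation, but only as a sensitivity analysis.

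A reader might also infer that nearly all risk is early, so that late dropouts carry none. The evidence is mixed. In section 4.2.2, PUFs supports it: 5.6% at 180 days, and at five years "the rate of major ipsilateral stroke or neurologic death remained 5.6" percent. ASPIRe (section 4.2.4) says "Most of the major adverse events (6.3%, 12/191) occurred in the early post-operative phase", but those are broader events with a median follow-up of 6.6 months. PREMIER (section 4.2.5) points the other way: no 30-day events due to procedural complications, yet 2.17% at 1 year. Timing governs the size of the bias, not its direction.

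SHIELD (section 4.2.7) is tempting as proof. At 30 days, events "were observed in 2.9% (6/204) of subjects", and the 1-year rate of 3.23% of 204 is 6.59 events, which suggests imputed fractions. However, the 30-day figure is limited to procedural complications. Reading 3.23% as 6/186 fails, since its exact interval is 1.19–6.89% against the printed 1.27–6.68%. SHIELD's ICA rate of 3.27% is exactly 5/153, with no fraction. SHIELD shows that imputing safety is conceivable, no more.

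Finally, any bias is conservative: it cannot make an unsafe device pass.

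**Conclusion.** The concern holds conditionally. The plan does not say whether section 13.4 governs primary safety. If it does, the estimate ignores event-free time and is biased upward.

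The effect is confined to the boundary: one event-free dropout is enough at 7 observed events, about 15 are needed at 6, and 5 or fewer events meet the rule with up to 20. With no events there is essentially nothing to inflate. At a true 5.6%, losing the seventh allowed event costs 13 percentage points of pass probability (80.2% to 67.2%).

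A reader might go on to the 51% figure, but that needs 15 or more late, event-free dropouts, and 20 is an imaging shortfall rather than loss of clinical follow-up. One-year clinical follow-up was 98.6% in PREMIER and 98.0% in PFLEX (section 4.2.8); SHIELD's 83.8% came from a study that did not require visits. With 1 or 2 dropouts a mean of 5.6% becomes only 5.66–5.71% (5.6 × 100/99 and 5.6 × 100/98).

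The 80% figure for an analysis that respects event-free time assumes that every event precedes every dropout. The other results assume uninformative baseline covariates and, for the bound after imputation, the pooling rule stated in step 2.

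**What to change.** Limit the baseline-only imputation of section 13.4 to the effectiveness endpoint. For primary safety, use event-free follow-up in the ITT set, by one of two routes:

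- Kaplan-Meier incidence at 1 year, censoring at the last contact known event-free (Aalen-Johansen if non-neurological deaths compete), with a prespecified 97.5% upper bound. Clopper-Pearson at an effective sample size is one option, and it reduces to the planned exact bound when nobody is censored.
- Multiple imputation conditional on the time event-free at last contact, with a stated pooling rule.

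Align the Synopsis, section 13.4 and section 13.8.2.2, and keep the last-observation and tipping-point analyses as sensitivity.

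Cost: a small wording change in the protocol as well as the SAP, because the Synopsis and section 13.8.2.2 fix the current rule. No extra data are needed beyond dates of event and last contact. The analysis would assume non-informative censoring, which the tipping-point analysis can probe. Kaplan-Meier can still slightly exceed 7% when a dropout precedes an event, so the team should decide in advance whether a result such as 7.01% fails Requirement 1.
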